3.3 Examination of Subject Subgroups

There are no prespecified subject subgroupings for efficacy and safety analyses.

3.4 Multiple Comparisons

Adjustments for multiplicity will not be made, because no formal statistical testing will be performed in this study.

3.5 Missing Data and Outliers

3.5.1 Missing Data

In general, missing data will not be imputed unless methods for handling missing data are specified.

The handling of missing or incomplete dates for disease diagnosis and prior anticancer therapy is described in Section 5.3; for prior and concomitant medications in described in Section 5.4; for new anticancer therapy is described in Section 6.1, for AE onset is described in Section 7.1.5.

3.5.2 Outliers

Outliers will be identified during the data management and data analysis process, but no sensitivity analyses will be conducted. All data will be included in the data analysis.

3.6 Data Handling Conventions and Transformations

In PK analysis, natural logarithm transformation will be used for serum concentration and analysis of PK parameters. Concentration values that are below the limit of quantitation (BLQ) will be presented as “BLQ” in the listing. Values that are BLQ will be treated as 0 at pre-dose timepoints, and one-half the value of the lower limit of quantitation (LLOQ) at postbaseline timepoints in the concentration summaries.

The following conventions will be used in the summary of concentration data:

- If at least 1 subject has a concentration value of BLQ for the timepoint, the minimum will be displayed as “BLQ”.
- If more than 25% of the subjects have a concentration value of BLQ for the timepoint, the minimum and Q1 values will be displayed as “BLQ”.
- If more than 50% of the subjects have a concentration value of BLQ for the timepoint, the minimum, Q1, and median values will be displayed as “BLQ”.
- If more than 75% of the subjects have a concentration value of BLQ for the timepoint, the minimum, Q1, median, and Q3 values will be displayed as “BLQ”.
- If all subjects have a concentration value of BLQ for the timepoint, all summary statistics (minimum, Q1, median, Q3, and maximum) will be displayed as “BLQ”.

3.7 Analysis Visit Windows

3.7.1 Definition of Study Day

Study day will be calculated from the first dosing date of any portion of the study drug:

- $\text{Postdose Study Days} = \text{Assessment Date} - \text{First Dosing Date} + 1$
- $\text{Study Day prior to First Dose} = \text{Assessment Date} - \text{First Dosing Date}$

3.7.2 Analysis Visit Windows

No analysis visit window will be assigned in the analysis as no summary by visit is planned.

3.7.3 Selection of Data

In general, the baseline value will be the last non-missing value on or prior to the first dosing date of study drug unless specified differently.

For continuous measurements, if multiple measurements occur on the same day, the last non-missing value will be considered as the baseline value. If these multiple measurements occur at the same time or the time is not available, the average of these measurements will be considered the baseline value. For categorical measurements, if multiple measurements occur on the same day, the last non-missing value will be considered as the baseline value. If these multiple measurements occur at the same time or the time is not available, the value with the lowest severity will be considered the baseline value.

Measurements occurred after first dose date will be considered postbaseline values.

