6.3 Administration and Preparation

6.3.1 FPA150

FPA150 will be administered as a 60-minute IV infusion Q3W in 21-day cycles until progressive disease or unacceptable toxicity. Proposed dose levels to be studied are outlined in [Table 3](#) for Phase 1a Dose Escalation. Please refer to the pharmacy manual for any additional dosing instructions for dose levels below 1 mg/kg.

The dose of FPA150 will be based on body weight at Cycle 1 Day 1. After Cycle 1, the FPA150 dose will be recalculated at each infusion visit only if the patient's weight has changed > 10% from Cycle 1, Day 1.

Further instructions on drug preparation and administration are in the Pharmacy Manual.

There is no pre-specified maximum number of doses of FPA150 monotherapy. Patients may continue receiving FPA150 according to their study specified cohort/ dose until Investigator-assessed clinical progression, unacceptable toxicity, or until the patient meets any of the other protocol-specified withdrawal criteria.

A pharmacist (or other responsible person) will prepare FPA150 for administration. After calculating the number of vials based on the patient's weight, FPA150 will be diluted in a 0.9% sodium chloride solution or 5% dextrose in water solution. Prepared FPA150 should be administered ≤4 hours after preparation under ambient temperature.

FPA150 will be administered under medical supervision over approximately 60-minute (± 5 minutes) IV infusion via a peripheral vein or central venous catheter. The IV administration set for FPA150 infusion must contain a 0.22 μm in-line filter or a 0.22 μm syringe filter.

All patients must be monitored for at least 4 hours after the end of the first infusion of FPA150. Patients in whom inpatient dose escalation is planned (ie, patients enrolled at dose levels below 1 mg/kg) should also be monitored for at least 4 hours after the end of infusion at each dose escalation. Infusion of FPA150 must be stopped, reduced, interrupted, or discontinued according to Section 6.4.4 (Dose Modification Criteria) and Section 6.4.6 (Dose Interruptions During Study Treatment Administration). If a patient experiences an infusion reaction, the patient's vital signs (temperature, blood pressure, pulse, and respiration rate) should be monitored during the infusion as well as every 30 minutes after the infusion for a minimum of 2 hours and until resolution of the infusion reaction.

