- e. Vital signs include pulse, respiratory rate, blood pressure, and temperature in a resting position. Measure vital signs prior to dosing and after completion of each IV infusion at the following time points: 5 minutes (± 3 min), 15 minutes (± 3 min), 30 minutes (± 3 min), and 1 hour post-dose (± 15 min). In addition, measure vital signs at 2, 3 and 4 hours post-dose (± 15 min) in patients that are being monitored for up to 4 hours post-dose (ie, after 1st infusion of FPA150 or after the end of infusion at each inpatient dose escalation).
- f. The exact time of the ECG should be recorded. The results will include heart rate, PR interval, QRS interval, QT interval, and QTc interval. Additional ECGs should be obtained at any time, if serum CK or cardiac troponin is elevated; if abnormal (excluding sinus tachycardia), ECGs should be obtained (if clinically indicated), until the abnormality is resolved or clinically stable. Additional ECGs may be obtained at any time, if clinically indicated. ECGs for each patient should be obtained from the same machine whenever possible. ECGs should be performed before the PK blood draw on days where both are done. To minimize variability, it is important that patients be in a resting position for at least 5 minutes prior to each ECG evaluation. Body position should be consistently maintained for each ECG evaluation to prevent changes in heart rate. Environmental distractions (eg, television, radio, conversation) should be avoided during the pre-ECG resting period and during ECG recording. Any clinically significant changes in ECGs that occur during the study should be reported as an AE in the eCRF.
- g. ECOG status is to be assessed at Screening, within 72 hours prior to dosing on Day 1 of each cycle, and at EOT.
- h. A biopsy will be collected from the primary tumor or metastatic tumor site in patients enrolled in Phase 1a Monotherapy Dose Exploration, and a subset of patients (15 patients per 30-patient dose cohort) in Phase 1b Monotherapy Dose Expansion and Phase 1b Combination Dose Expansion cohorts; this will be done at screening and prior to the Cycle 3, Day 1 dose, from the same lesion where feasible. Refer to Section 8.4 for details regarding analyses of tumor tissue (fresh or archival).

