7.3 Body Weight and Vital Signs

Descriptive statistics will be provided by treatment group for body weight and vital signs as follows:

- Baseline
- Postbaseline maximum
- Postbaseline minimum
- Change and percentage change from baseline to postbaseline maximum
- Change and percentage change from baseline to postbaseline minimum

A baseline value is defined as the last available value collected on or prior to the first dose of study drug.

A by-subject listing of body weight and vital signs will be provided by subject ID and time point in chronological order.

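### SAP 3.7.3 defines post-baseline by date, so vital signs taken after the infusion on Cycle 1 Day 1 drop out of the maximum, minimum and change summaries

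*SAP*

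**What the plan says.** SAP 3.7.3 sets the general baseline as "the last non-missing value on or prior to the first dosing date of study drug unless specified differently". If a continuous variable is measured more than once that day, the last value is used. It then defines the other side: "Measurements occurred after first dose date will be considered postbaseline values". The SAP defines post-baseline nowhere else.

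SAP 7.3 has its own baseline sentence for weight and vital signs: "A baseline value is defined as the last available value collected on or prior to the first dose of study drug". The summaries it plans include the post-baseline maximum and minimum and the changes to each, for example "Change and percentage change from baseline to postbaseline maximum". It does not say what post-baseline means. No table by visit fills the gap, because SAP 3.7.2 states: "No analysis visit window will be assigned in the analysis as no summary by visit is planned".

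Protocol Appendix 1, footnote e, says: "Measure vital signs prior to dosing and after completion of each IV infusion at the following time points", and lists 5, 15 and 30 minutes and 1 hour. It goes on: "In addition, measure vital signs at 2, 3 and 4 hours post-dose", for patients under 4-hour observation, which includes everyone after the first infusion. Protocol 6.3.1 makes that observation compulsory: "All patients must be monitored for at least 4 hours after the end of the first infusion of FPA150".

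**The concern.** Every vital sign taken after the infusion on Cycle 1 Day 1 carries the first dose date, so none of them is after that date. A programmer who follows SAP 3.7.3 will leave them all out of the post-baseline maximum and minimum. The same applies to the extra half-hourly readings that Protocol 6.3.1 requires when a patient reacts to the infusion, if the reaction comes at the first dose.

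This is a first-in-human antibody, and Protocol 6.4.6 names fever, hypotension and hypertension among the possible infusion-reaction symptoms. A summary without the first infusion could show little change even if blood pressure, pulse, temperature or respiration moved markedly after that dose. Changes that were not reported as adverse events would then appear in no table.

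There is also a smaller inconsistency. SAP 3.7.3 sets baseline by dosing date, while SAP 7.3 sets it by the first dose. The natural reading of 7.3 keeps the pre-dose value, but the two sentences should agree.

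**Working it through.** The plan gives no figure to reproduce. The check applies the SAP rules to the protocol schedule and counts the readings affected.

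**Classifying a Cycle 1 Day 1 post-infusion reading**

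- Baseline under SAP 7.3? No. It was taken after the first dose.
- Post-baseline under SAP 3.7.3? No. It was taken on the first dose date, not after it.
- If the 7.3 baseline were instead read by date, as in 3.7.3, the last reading of the day (about 4 hours after the infusion) would become baseline. Change would then be measured from a value on drug, and the day's readings would still not be post-baseline.

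**Counting scheduled sets after the first dose** (monotherapy, no intrapatient escalation, both End of Treatment visits attended; Protocol Appendix 1, schedule table and footnote e)

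- Cycle 1 Day 1, after infusion: 5, 15, 30 minutes and 1, 2, 3, 4 hours = 7
- Cycle 1 Day 8: 1
- Each later dosing day: 1 pre-dose + 4 post-infusion = 5
- End of Treatment, day 28 and day 100: 2

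Total for *d* doses = 7 + 1 + 5(*d* − 1) + 2. Omitted = 7. Post-infusion sets only = 7 + 4(*d* − 1).

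| Doses | Total sets | Kept | Omitted, all sets | Omitted, post-infusion sets only |
|---|---|---|---|---|
| 1 | 7 + 1 + 0 + 2 = 10 | 3 | 7/10 = 70% | 7/7 = 100% |
| 3 | 7 + 1 + 10 + 2 = 20 | 13 | 7/20 = 35% | 7/15 = 47% |
| 11 | 7 + 1 + 50 + 2 = 60 | 53 | 7/60 = 12% | 7/47 = 15% |

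Three doses is the Phase 1a median and 1 to 11 the range, in 24 patients at the 31 December 2018 cut-off (Protocol 2.2.5.3). This is not final exposure. Combination patients lose at least seven sets, because footnote e asks for readings after each infusion and they receive two.

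**Illustration with assumed systolic values.** Pre-dose 120; lowest Cycle 1 Day 1 post-infusion value 85, recovering to 118 at 4 hours; lowest later value 118.

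- SAP 7.3 baseline with SAP 3.7.3 post-baseline: minimum 118, change 118 − 120 = −2.
- Baseline taken as the last value of the day: baseline 118, change 118 − 118 = 0.
- Split at the start of the first infusion: minimum 85, change 85 − 120 = −35.

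**Other safety data.** Laboratory tests, weight and ECG are little affected, since no post-infusion reading of these is scheduled on Cycle 1 Day 1.

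**The case against.** The strongest reply is that this is loose wording, not an exclusion. SAP 3.7.3 does not contain the word *only*. SAP 7.3 overrides the general baseline, and post-baseline in that section could be read as anything after that baseline. Other text leans the same way. SAP 3.6 handles PK values below quantitation as either pre-dose or post-baseline, which covers the Cycle 1 Day 1 post-infusion PK samples only if post-baseline includes them. SAP 3.7.1 makes the first dosing date Study Day 1. The tie-break rules in 3.7.3 refer to measurement time.

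A careful programmer might indeed use clock time, but none of these passages defines post-baseline for vital signs. SAP 3.6 concerns PK concentrations, 3.7.1 numbers study days, and the tie-breaks choose a baseline value. The one sentence that does define the term goes by date.

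Three parts of the reply stand:

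- The omitted share equals the chance of missing a patient's true extreme only if all readings are exchangeable. Seven readings within four hours are clustered while the others span weeks, so that is doubtful, and the documents have no data to settle it. The shares are best read as counts.
- A corrected table would still pool all visits, so it would not show the first infusion separately.
- The consequence is modest. The listing keeps every reading (SAP 7.3), reactions count as treatment-emergent events (SAP 7.1.6), infusion interruptions are summarised (SAP 4.2), and dose decisions lay with the Cohort Review Committee, not with this table.

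**Conclusion.** The concern holds. Followed as written, SAP 3.7.3 and 7.3 together leave all seven scheduled Cycle 1 Day 1 post-infusion sets out of the vital-sign summaries. For monotherapy with full attendance and no intrapatient escalation, that is 35% of scheduled sets after the first dose at three doses, between 70% (one dose) and 12% (eleven doses). The conclusion rests on reading the date rule literally, which is the only rule the SAP gives. It does not touch a primary endpoint or a dose decision. It does make a safety table misleading about the infusion with the longest scheduled vital-sign monitoring, and it should be corrected.

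**What to change.** Use one definition in SAP 3.7.3 and 7.3:

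- **Baseline:** the last non-missing value before the start, by date and time, of the first infusion.
- **Post-baseline:** any value after that start, including the Cycle 1 Day 1 post-infusion readings.
- **Missing clock time:** classify by nominal time point, pre-dose or post-dose.

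This also removes the mismatch between the two baseline sentences. The cost is two SAP sentences and a small programming change. The time points are already collected, and there is no real downside. If the SAP is already final, Protocol 9.3 provides for the change to be described and justified in the clinical study report.

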4 SUBJECT DISPOSITION

4.1 Subject Enrollment and Disposition

A summary of subject disposition will be provided by treatment group. Percentages will be based on the Safety Analysis Set. The number of subjects in the following categories will be provided:

- Signed the informed consent
- Received any study treatment
- Continuing study treatment
- Discontinued from study treatment with reasons for treatment discontinuation
- Continuing study
- Discontinued from study with reasons for study discontinuation

4.2 Extent of Exposure and Adherence

Descriptive statistics of extent of exposure will be presented by treatment group for FPA150:

- Duration of exposure (weeks)
- Cumulative exposure by week
- Number of infusions

Total duration of exposure to study drug (in weeks) will be defined as (last available dosing date – first dosing date + 21)/7, regardless of any temporary interruptions in study drug administration.

The number and percentage of subjects who have dose reduction, dose delay or interruption, and infusion interruption will be summarized with reasons.

Summaries of exposure will be performed with the Safety Analysis Set. A by-subject listing of study drug administration will be provided.

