Dosing: FPA150 will be administered as a single agent in a 60-minute (± 5 minutes) IV infusion Q3W, on Day 1 of each 21-day cycle. The dose of FPA150 will be based on body weight at Cycle 1 Day 1 (C1D1). After Cycle 1, the FPA150 dose will be recalculated at each infusion visit only if the patient's weight has changed $> 10\%$ from Cycle 1, Day 1. There is no pre-specified maximum number of doses of FPA150 for patients receiving monotherapy.

Patients may continue receiving FPA150 monotherapy according to their study specified cohort/dose until Investigator-assessed clinical progressive disease, unacceptable toxicity, or the patient meets any of the other protocol-specified withdrawal criteria (refer to Section 7).

For combination cohorts, pembrolizumab will be administered at a dose of 200 mg IV over 30 minutes (\pm 5 minutes) starting on C1D1 after the completion of FPA150 infusion. Dosing for combination cohorts will be repeated on Day 1 of each 21-day cycle. Patients in the combination cohort may receive one or both drugs in combination according to their study specified cohort/dose until Investigator-assessed clinical progressive disease, unacceptable toxicity, or the patient meets any of the other protocol-specified withdrawal criteria (refer to Section 7). Patients treated with the combination would be able to receive pembrolizumab treatment for up to 24 months. If one of the two drugs has to be discontinued, patients may continue to receive the other drug alone.

Treatment beyond disease progression may be allowed in patients with progressive disease according to Response Evaluation Criteria in Solid Tumors version 1.1 (RECIST v1.1) if the benefit/risk assessment favors continued administration of study treatment (eg, if patients are continuing to experience clinical benefit as assessed by the Investigator, and tolerating treatment).

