6.5 Maximum Duration of Treatment

There is no pre-specified maximum number of doses of FPA150 monotherapy or in combination. Patients may continue receiving FPA150 monotherapy according to their study specified cohort/dose until Investigator-assessed disease progression or the patient meets any of the other protocol-specified withdrawal criteria.

Patients may receive pembrolizumab therapy according to their study specified cohort/dose until Investigator-assessed disease progression, the patient meets any of the other protocol-specified withdrawal criteria or the patient completes approximately 24 months of pembrolizumab treatment.

If one of the two drugs have to be discontinued, patients may continue to receive the other drug alone.

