
FPA150 in Combination with Pembrolizumab
 
 • To evaluate the clinical benefit of FPA150 in combination with pembrolizumab in patients with B7-H4 + ovarian cancer treated at the MTD and/or RD 	
FPA150 in Combination with Pembrolizumab
 
 • ORR, defined as the total number of patients with confirmed responses of either CR or PR per Response Evaluation Criteria in Solid Tumors (RECIST) v1.1 divided by the total number of patients who are evaluable for a response to FPA 150 combined with pembrolizumab • DOR, defined as the time from onset of response (CR or PR) that is subsequently confirmed to the first observation of progressive disease or death due to any cause to FPA150 combined with pembrolizumab • PFS, defined as the time from the patient's first dose to the first observation of progressive disease or death due to any cause to FPA150 combined with pembrolizumab
SECONDARY - PHARMACOKINETICS	

FPA150 Monotherapy
 
 • To characterize the PK profile of FPA150 as monotherapy in patients with B7-H4+ advanced solid tumors treated at the MTD and/or RD 	
FPA150 Monotherapy
 
 • AUC • C_{max} • C_{trough} • CL • t_{1/2} • V_{ss} • Other parameters, such as accumulation ratio, attainment of steady state, will also be calculated if the data are available

OBJECTIVES	ENDPOINTS
SECONDARY - IMMUNOGENICITY	

FPA150 Monotherapy
 
 To characterize the immunogenicity of FPA150 as monotherapy in patients with B7-H4+ advanced solid tumors treated at the MTD and/or RD 	
FPA150 Monotherapy
 
 Immune response (ADAs) to FPA150
EXPLORATORY - PHARMACOKINETICS	

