3.1.2 Efficacy-Evaluable Analysis Set

The Efficacy-Evaluable Analysis Set includes all subjects received at least 1 dose of FPA150, had at least 1 postbaseline evaluable tumor assessment unless death or clinical progressive disease occurred prior to the first post baseline disease assessment.

The Efficacy-Evaluable Analysis Set will be used in the summary of efficacy data.

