6.1 Objective Response Rate

ORR is defined as the proportion of subjects who achieve best overall response (BOR) of either complete response (CR) or partial response (PR) based on investigator assessment tumor lesions per RECIST v1.1. The BOR is the best response documented from first dose until the end of study, first disease progression, death, or start of new anti-cancer therapy, whichever is earlier. Subjects, who do not have sufficient baseline or on-study tumor status information to be adequately assessed for response status (i.e., those with BOR of not evaluable [NE]), or received anticancer therapy other than the study treatment, will be considered as non-responders and will be included in the denominators in calculations of response rates.

When the date of initiation of new anticancer therapy other than the study treatment is incomplete or missing, the following algorithm will be followed:

- If the day is missing but the month and year are available, then the imputed day will be the last day of the month.
- If day and month are missing but year is available, then the imputed day and month will be the last day of the month for the last adequate disease assessment if they have the same year.

The analysis of ORR will be performed based on the Efficacy-Evaluable Analysis Set. ORR with corresponding 2-sided 95% CI based on Clopper-Pearson method along with each category of BOR will be summarized by treatment group. Patients who don't have any postbaseline adequate tumor assessments will be counted as non-responders.

By-subject listings will be provided for target lesion, nontarget lesion, new lesion, and investigator-assessed timepoint response. A by-subject listing of new anticancer therapy will also be provided.

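### For the combination group the SAP summarises exposure and AE-related stops for FPA150 only, and does not mark responses first documented after one drug has stopped

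*SAP*

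**What the plan says.** **Treatment.** Protocol 6.5, on the combination: "If one of the two drugs have to be discontinued, patients may continue to receive the other drug alone". The synopsis says the same. Pembrolizumab may run for about 24 months.

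**Exposure.** SAP 4.2: "Descriptive statistics of extent of exposure will be presented by treatment group for FPA150". The items listed are duration, cumulative exposure by week and number of infusions. A separate sentence promises counts of patients with dose reductions, delays and interruptions, with reasons, and names no drug. The section ends with a by-subject dosing listing.

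**Adverse events.** SAP 7.1.6 limits the discontinuation table to TEAEs that led to stopping FPA150. Protocol 9.4.1 plans a summary of AEs leading to discontinuation without naming a drug.

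**Response.** In SAP 1.2.2 the Phase 1b combination ORR is the number of confirmed responders "divided by the total number of patients who are evaluable for a response to FPA 150 combined with pembrolizumab". SAP 6.1 takes the "best response documented from first dose until the end of study, first disease progression, death, or start of new anti-cancer therapy", whichever is earliest. The one rule there that turns on treatment is that patients who "received anticancer therapy other than the study treatment, will be considered as non-responders". On entry to the analysis, SAP 3.1.2 says: "The Efficacy-Evaluable Analysis Set includes all subjects received at least 1 dose of FPA150"; it also asks for a post-baseline tumour assessment, with an exception for early death or clinical progression.

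**The concern.** The combination group receives two drugs and the plan allows them to be stopped separately, but the tables that describe how treatment was received follow only one of them.

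This matters most for tolerability, a primary objective for the combination in both phases. Protocol 6.4 does not permit pembrolizumab dose reductions, and 6.4.5 has immune-related events managed partly by interrupting the drug. Delays and stops are therefore the main dose-related sign of how well pembrolizumab is tolerated alongside FPA150. Those are the figures the SAP does not specify for it.

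There is a smaller consequence for efficacy. The endpoint is described as response to the two drugs combined, yet the response window stays open when one of them stops. A reader of the BOR table cannot tell which responses were first seen while both drugs were being given. SAP 6.3 drops DOR and PFS, so this is the main efficacy table left.

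**Working it through.** **1. What each planned output shows for the combination group**

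| Output | FPA150 | Pembrolizumab |
|---|---|---|
| Duration, cumulative exposure, infusions (SAP 4.2) | named | not named |
| Reduction, delay, interruption counts (SAP 4.2) | drug not stated | drug not stated |
| Discontinued treatment, with reasons (SAP 4.1) | one undivided row | one undivided row |
| TEAEs leading to discontinuation (SAP 7.1.6) | named | not named |
| DLT summary (SAP 7.1.7) | yes | lead-in only, because protocol 6.4.5 makes toxicity-driven pembrolizumab modifications DLTs |
| Dosing listing (SAP 4.2) | yes | yes, if study drug covers both, as SAP 7.1.3 implies |

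In Phase 1b, no table is specified that gives pembrolizumab infusions, duration or AE-related stops.

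**2. What the exposure table would hide.** SAP 4.2 defines duration in weeks as (last dose date − first dose date + 21)/7. As an illustration (my assumption), take nine 21-day cycles with no delays.

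- Patient A has nine doses of both drugs. FPA150 duration is (8 × 21 + 21)/7 = 27 weeks, with 9 infusions.
- Patient B stops pembrolizumab after one dose and has nine FPA150 doses. FPA150 duration is again 27 weeks, with 9 infusions.
- Patient C stops FPA150 after one dose and has nine pembrolizumab doses. FPA150 duration is (0 + 21)/7 = 3 weeks, with 1 infusion.

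The table cannot tell A from B, and it shows C as leaving treatment after 3 weeks. Time on both drugs is 27, 3 and 3 weeks.

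**3. Whether a late response counts.** Under SAP 6.1 the window closes at end of study, first progression, death or new anticancer therapy. Stopping one component is none of these. The non-responder rule applies only to therapy from outside the study, and the remaining component is study treatment. A first response on either drug alone therefore enters the combination ORR. SAP 3.3 plans no subgroups, and no flag or sensitivity analysis separates these cases.

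**4. How much one response weighs.** The plan's own figures reproduce.

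- Early termination at a true rate of 0.05: P(≤1 of 16) = 0.95^16 + 16 × 0.05 × 0.95^15 = 0.440 + 0.371 = 0.811, against 0.81 stated.
- 90% Clopper-Pearson at n = 25: 5/25 gives 8.2% to 37.5% and 6/25 gives 11.0% to 42.0%. These match protocol Table 11 and SAP Table 7 after rounding.

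Against the plan's reference points:

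- The early-look criterion is met at 1/16 and not at 2/16.
- The 90% lower bound passes 10% between 5/25 (8.2%) and 6/25 (11.0%).
- SAP 6.1 will report 95% intervals. There the passage is between 6/25 (9.4%) and 7/25 (12.1%).
- SAP 3.2 pools lead-in and Phase 1b combination patients at the same dose. With up to 10 + 30 = 40 patients, the 95% bound passes 10% between 8/40 (9.05%) and 9/40 (10.8%).

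One response is 1/25 = 4 percentage points, or 1/40 = 2.5. Two in 25 would be 8 points. The documents give no rate of single-drug continuation, so these figures show the weight of one case and do not estimate how many there will be.

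**The case against.** A reader might infer that a pembrolizumab-alone response could decide the combination result without anyone seeing it. The documents do not support that.

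- **Listings exist.** SAP 4.2 ends with a dosing listing not confined to FPA150, and SAP 6.1 lists timepoint responses by patient. With no more than 30 patients in a cohort, matching the two by hand is feasible.
- **Nothing binding follows.** SAP 3.4 says there is no formal testing, and under SAP 1.3 the sponsor may, not must, suspend a cohort. The 5/25 to 6/25 crossing belongs to the 90% planning interval, not to the 95% interval to be reported.
- **Not every response counts.** Those after first progression or new anticancer therapy are excluded.
- **Patients who never received pembrolizumab.** SAP 3.1.2 requires only FPA150, but SAP 3.2 groups by treatment actually received, so on its face such a patient is not in the combination group.

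A reader might also infer that overlap in exposure would separate the combination effect from single-agent activity. It would not. The trial has an FPA150-alone ovarian cohort (1b2) but no pembrolizumab-alone arm, so even a response on both drugs cannot be credited to the combination.

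Nor do the documents support recoding late responses as non-responses. Protocol 4.6 expects a half-life of about 10 to 20 days, and scans are 6-weekly for six months and 12-weekly afterwards. A response that began under both drugs may first be documented after one has stopped, with antibody still present. Counting responses under the assigned regimen, including permitted continuation on one drug, is a legitimate choice.

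All of these objections stand. They do not reach the narrower point. A listing is not a summary, the disposition row is undivided, the delay sentence is at best ambiguous about the drug, and the lead-in DLT rule does not extend to Phase 1b.

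**Conclusion.** The point holds as a reporting gap, and it is cheap to close. Followed as written, the SAP under-reports pembrolizumab exposure and stops for a combination whose tolerability is a primary objective, and its discontinuation table is narrower than the one in protocol 9.4.1. Responses first documented after one drug has stopped count in the combination ORR and are not marked in any summary table, though the listings allow them to be traced.

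The number of patients affected is unknown. Per case the weight is 4 percentage points of ORR at 25 patients and 2.5 at 40. That can move an interval across 10% only when the count already sits next to the crossing.

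The conclusion rests on two readings: that the words limiting SAP 4.2 to FPA150 are meant literally, and that the dosing listing covers both drugs. If the second is wrong, the gap is larger. The documents do not show that the planned ORR is wrong, or that a single-drug response would settle the cohort's fate.

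**What to change.** - **SAP 4.2, combination group:** give the same summaries for pembrolizumab (infusions, duration, delay or interruption, and discontinuation, each with reasons), and add the duration on both drugs. State which drug each delay or interruption count refers to.
- **SAP 7.1.6:** add tables of TEAEs leading to discontinuation of pembrolizumab and of either drug.
- **SAP 6.1:** keep the planned ORR. In the BOR table or listing, flag any responder whose response was first documented after permanent discontinuation of either drug, and name the drug. Do not recode the response as a non-response.

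The SAP governs only the final analysis, so nothing here changes the 16-patient look. No treatment rule changes either. Protocol 6.9 already puts the date, time and dose of each administration on the eCRF, so no new dosing data are needed.

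The cost is one exposure block, two AE tables and a flag. Counting stops of either drug may also raise the reported discontinuation rate.
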